8.1.8. Migraine-ACT Questions (Assessment of Current Therapy)

The frequencies and percentages will be provided for all subject responses on the ACT by visit. Note that if a subject has not treated any migraine attacks since the most recent in clinic study visit, the ACT response will be missing. Missing data will not be imputed.

9. ANALYSIS OF PHARMACOKINETICS

Not Applicable

10. ANALYSIS OF PHARMACODYNAMICS

Not Applicable

11. SAFETY

Safety will be assessed through the following:

- Physical examination findings including height (at screening and final visit only) and weight,
- Vital signs including blood pressure,
- Clinical laboratory determinations including serum chemistries and hematological parameters,
- 12-lead ECGs,
- Assessment of concomitant medications,
- All treatment-emergent systemic and skin AEs (TEAEs),
- Subject reported Skin Assessment, and
- Investigator Skin Assessment.

All safety analyses will be based on the Safety Population. Adverse events will be coded using the current Medical Dictionary for Regulatory Activities (MedDRA) dictionary (version 20.0 or higher) and will be summarized overall and by preferred term and system organ class. Adverse events will also be summarized by severity and relationship to study drug. Serious AEs and AEs leading to discontinuation of study drug will also be summarized.

Clinical laboratory test results and ECG parameters will be summarized at each visit using shift tables or listings of abnormal results as appropriate. The number and percentage of subjects experiencing Bruising, Erythema, Edema and other skin assessments will also be summarized.

All data gathered will be listed by patient and parameter, separate listings of all abnormal laboratory findings will be provided, and clinically significant abnormalities will be recorded as AEs.

11.1. EXTENT OF EXPOSURE AND COMPLIANCE

Treatment duration will be calculated as (number of days=last dose date - first dose date+1). First and last dose dates will be determined from the dates of patch application recorded in the eDiary. Average treatment duration per subject in days will be summarized. Frequencies of duration, 0-6 months, 6-12 months, and >12 months will be provided.

Study drug exposure will be captured as the total number of doses. Patch application is captured in the eDiary, and a subject is considered as having received one dose regardless if one or two patches are applied. The average number of treated migraines per month per subject for months 1-12 and overall will also be summarized, as well as frequencies provided for ≥ 12 doses and ≥ 24 doses. Also, the frequency of the number of subjects with at least 2 doses per month on average for at least 6 months will be provided.

Compliance will be assessed as the percentage of subjects treating at least 2 migraines per month. Months will be defined starting with the day IP was provided to the subject and calculated as each consecutive 30-day period following the day IP was first provided.

All study drug dosing information will be listed.

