 - Subject reported skin assessment for bruising, swelling, and/or redness (at 30 minutes, 2 hours, 12 hours, 24 hours and 48 hours post patch administration time points only)
 - Subject reported skin pain and skin itching at 48 hours post patch administration
- Dispense the Subject Skin Grading Card (Appendix 4) with the eDiary and instruct the subject to refer to this card when grading their skin reaction(s)/symptom(s) in the eDiary. The Grading Card will include a subject reminder to contact the study physician if he/she experiences any serious or severe skin reaction(s) at any time point or for worsening or non-resolving reactions at approximately 3 days post patches application (at 72 hours). In addition, the eDiary will remind the subject to call the study physician if he/she experiences any skin reaction(s) and/or symptom(s) at the patch application site which worsens rather than improves over approximately a five-day period. If the subject

contacts the study physician at any time point for worsening or non-resolving reactions, the subject must be seen for an unscheduled visit. The skin reaction(s)/symptom(s) will be assessed, recorded as an adverse event in the eCRF and followed to resolution.

6.1.5 Month 1 (Visit 4), Month 2 (Visit 5), Month 3 (Visit 6), Month 6 (Visit 7)

Visits must be scheduled to occur on (or within ± 7 days) of the protocol specified study day, ie, on study days 28 (Month 1), 56 (Month 2), 84 (Month 3), and 168 (Month 6). The following procedures will be performed at each visit:

- Administer the Migraine Assessment of Current Therapy (Migraine-ACT) which is completed by the subject
- Collect any unused patches, perform accountability, and dispense patches with applicator
- Perform physical exam, (Month 6 only) (height does not need to be recorded)
- Record vital signs: temperature, respiratory rate (RR), blood pressure (BP), and heart rate (HR)
- Collect urine for urine pregnancy test for all WOCBP
- Collect urine for drug abuse testing (Month 6 only)
- Perform 12-lead electrocardiogram (ECG) (Month 6 only)
- Ensure subject is dispensed the Subject Skin Grading Card (to be used with eDiary entries).
- Collect and review subject's eDiary data with the subject for the following:
 - Subject compliance with study drug treatment and subject responses in eDiary

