- Perform Investigator Skin Assessment (presence of blisters, scaly or flakey skin, erosions or open sores, scarring, hyperpigmentation, bruising, redness, and/or swelling) of upper arm where patches have been applied
- Any cutaneous signs or symptoms found on the investigator skin assessment will be recorded as an adverse event on the eCRF and followed to resolution.
- Record concomitant medications
- Record adverse events. In addition, any skin reaction(s) entered into the eDiary by the subject must also be recorded as an adverse event in the eCRF and followed to resolution.

6.1.6 Month 9 (Visit 8) and Month 12 End of Study Final Visit (Visit 9/or Early Termination)

The Month 9 and 12 visits are to be scheduled on (or within ± 7 days) of the protocol specified study day, i.e., on study days 252 (Month 9) and 336 (Month 12). The following procedures will be performed. If a subject terminates early from the study at any time after applying M207, an Early Termination visit must be scheduled to occur within 7-14 days after the subject's last patch application.

- Administer the Migraine Assessment of Current Therapy (Migraine-ACT) to be completed by the subject
- Collect the applicator, any unused patches, and perform accountability
- Dispense M207 patches (Month 9 only)
- Perform physical exam, including weight and height (Month 12 final visit/or early termination only)
- Record vital signs: temperature, respiratory rate (RR), blood pressure (BP), and heart rate (HR)
- Collect blood (4-hr fasting) for clinical laboratory measurements including clinical chemistries and hematology (Month 12 final visit/or early termination only)
- Collect urine for urine pregnancy test for all WOCBP
- Perform 12-lead electrocardiogram (ECG) (Month 12 final visit/or early termination only)
- Ensure subject is dispensed a Subject Skin Grading Card (at Month 9 only)
- Collect and review subject's eDiary data with the subject for the following:
 - Subject compliance with study drug treatment and subject responses in eDiary
- Perform Investigator Skin Assessment (presence of blisters, scaly or flakey skin, erosions or open sores, scarring, hyperpigmentation, bruising, redness, and/or swelling) of upper arm where patches have been applied
- Any cutaneous signs or symptoms found on the investigator skin assessment will be recorded as an adverse event on the eCRF and followed to resolution.
- Record concomitant medications

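### SAP 11.1 counts 30-day months on a 28-day visit calendar, so Month 12 has at most 13 observable days for an in-window completer, and the duration classes have no day cut-points

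*SAP*

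**What the plan says.** **Month length.** For compliance, SAP 11.1 starts months on the day study drug was provided, "calculated as each consecutive 30-day period following the day IP was first provided". The same section asks for the average number of treated migraines per subject in months 1 to 12, and measures compliance as the percentage of subjects treating at least two migraines per month.

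**Duration.** "Treatment duration will be calculated as (number of days=last dose date - first dose date+1", with both dates taken from the eDiary. Then: "Frequencies of duration, 0-6 months, 6-12 months, and >12 months will be provided". No month length is attached to these classes. Separately, "Study drug exposure will be captured as the total number of doses".

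**Visit calendar.** Protocol 6.1.5 and 6.1.6 place the visits "on study days 28 (Month 1), 56 (Month 2), 84 (Month 3), and 168 (Month 6" and "on study days 252 (Month 9) and 336 (Month 12", each with a window of ± 7 days. Protocol 6.1.4 makes Visit 3, when patches are first dispensed, Day 1. Protocol Table 10 and SAP Table 1 both print Month 6 as Week 24 and Month 12 as Week 48.

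**End of dosing.** Protocol 6.1.6 tells the site to "Collect the applicator, any unused patches, and perform accountability", and patches are dispensed again at Month 9 only. Dosing therefore ends at the final visit.

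SAP 13, which lists changes from the protocol, does not mention month length. SAP 7.1 reports the numbers completing 6 and 12 months separately.

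**The concern.** The SAP's month and the schedule's month differ by two days. Over twelve months the gap grows to 24 days, and it falls almost entirely on the last month. A Month 12 row built on the 30-day rule would describe a period most of which lies after the patches have been handed back. Without a rule for partly observed months, use and compliance would appear to collapse at the end of treatment, and a reader could take that for loss of interest or tolerability.

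The duration classes raise a smaller, related point. The study plans 6 to 12 months of treatment, and the class line is where a reader looks for long exposure. As written, it cannot show who reached the planned end of treatment.

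**Working it through.** **1. Reproduce the schedule.** 28 × 1, 2, 3, 6, 9 and 12 gives 28, 56, 84, 168, 252 and 336, which are the protocol's days exactly. Also 48 weeks × 7 = 336.

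**2. Observable part of the 30-day Month 12.** Month k covers Days 30(k − 1) + 1 to 30k, so Month 12 is Days 331–360. An in-window final visit falls on Days 336 − 7 = 329 to 336 + 7 = 343.

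| Final visit | Observable days of Month 12 |
|---|---|
| Day 329 | 0 |
| Day 336 | 336 − 330 = 6 |
| Day 343 | 343 − 330 = 13 |

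If months are taken to start on the day after dispensing, the figures are 0, 5 and 12, so 13 is the maximum on either reading. Month 11 (Days 301–330) is hardly affected: with a Day 329 visit, 29 of its 30 days are observed.

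**3. Effect on the Month 12 row if partial months are kept.** Illustration only. Assume Poisson attacks, all treated, at 2, 4 or 8 per 30 days; these rates span the 2–8 per month entry range. With mean m = rate × days / 30, P(at least 2) = 1 − exp(−m)(1 + m).

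| Days observed | 2 per 30 d | 4 per 30 d | 8 per 30 d |
|---|---|---|---|
| 6 | 6% | 19% | 48% |
| 13 | 22% | 52% | 86% |
| 30 | 59% | 91% | 99.7% |

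For example, 4 per 30 days over 6 days gives m = 0.8 and 1 − exp(−0.8) × 1.8 = 0.191. The mean Month 12 count is 0.8 instead of 4. Adding the protocol's 48-hour gap between treated attacks (by simulation) gives 3% / 9% / 25% for 6 days and 55% / 89% / 99.5% for 30 days, so the contrast remains.

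**4. Longest dosing span.** First dose on Day 1 and last dose on Day 343 gives 343 − 1 + 1 = 343 days.
- 30-day months: 12 × 30 = 360, and 343 < 360.
- Calendar months: 343 < 365.
- 28-day months: 12 × 28 = 336, so the top class is open only to final visits on Days 337–343. A completer seen exactly on Day 336 cannot enter it.

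A final visit would have to fall on Day 361, 18 days after the window closes, to exceed 360 days.

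**5. Why dose dates alone do not identify completers.** First-to-last-dose duration loses time at both ends. Let q = exp(−rate/30). For a Day 336 completer, the chance that the span reaches 329 days is 1 − q⁸ − 8(1 − q)q⁸, which is 11% / 31% / 66% at the three rates. Explicit cut-points on that measure are needed for clarity, but they will not show who reached the end of treatment.

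**The case against.** The strongest reply is that nothing printed in SAP 11.1 is numerically wrong. The duration classes merely lack a month length, and the 30-day sentence sits in the compliance paragraph. An empty top class would be truthful: 343 days of dosing is not more than 12 calendar months, and an open class still catches late visits. Completion is tabulated in SAP 7.1. The Month 12 effect needs results to be computed month by month with partial months kept. The compliance wording could mean an average, and the table shells, a separate document, may hold a rule.

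Much of this stands, and it limits the point. A reader might infer three stronger things that the documents do not support:

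- *That one-year exposure, or the counts against the targets of 150 and 50, would be lost.* They would not. Disposition, mean days, dose counts and listings do not depend on the classes.
- *That subjects who stop at Month 6 are misclassified.* An in-window Month 6 visit allows at most 175 days, which is below 180, but the class month is undefined. A span of 175 days is also correctly under six calendar months, and completing a visit is a different quantity from duration of dosing. The schedule has no planned exit at Month 6, and the number of such stoppers is unknown.
- *That the Month 12 bias is certain.* It is conditional, as stated above.

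What the reply does not remove is the conflict over Month 12. SAP 11.1 asks for months 1 to 12, and SAP Table 14.3.2.5 is titled as a per-month display. The one month length given contradicts the SAP's own schedule.

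**Conclusion.** The point holds as a conflict between the month definition in SAP 11.1 and the visit schedule. The 0–13 observable days in Month 12 (6 at Day 336) and the 343-day maximum span are calendar bounds. They rest only on in-window visits, on dosing ending at the final visit, and on Day 1 being Visit 3. SAP 6.2.3 counts study day from first administration. If the final-visit window were counted that way, the 343-day maximum would stand, but Month 12 could gain days equal to the delay before the first dose. The protocol's anchor at Visit 3 argues against that reading.

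The downward bias in Month 12 use and compliance follows if monthly results are tabulated as written and no rule for partial months exists elsewhere. Its size (19% against 91% at 4 attacks per 30 days) depends on the assumed model and is an illustration. The duration-class point is secondary and concerns presentation. Taken together, this ranks between a minor point and one that should be fixed.

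**What to change.** In SAP 11.1:

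1. Define a month as 28 days from Visit 3. Months 1–11 are Days 1–308 (11 × 28), and Month 12 runs from Day 309 to the final visit, so that doses on Days 337–343 are counted. Report treated migraines per 28 observed days. Count a subject-month for compliance only if it is fully observed or ended by an in-window scheduled visit.
2. Give the duration classes explicit, non-overlapping day cut-points and keep the first-to-last-dose measure. Add one row for time from Visit 3 to the final or early-termination visit, with its top class starting at the Month 12 window (329 days or more).

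The cost is SAP wording and minor table-shell edits; no visit, dose or data item changes. There are three downsides:

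- Month 12 varies from 329 − 308 = 21 to 343 − 308 = 35 days for in-window completers. At an assumed 2 attacks per 30 days, the chance of two or more runs from 41% (21 days) to 68% (35 days). A footnote should say how many counted months differ from 28 days.
- Two per month is slightly harder to meet on 28 days: 56% against 59% at the same rate.
- Protocol 6.1.6 says the "Early Termination visit must be scheduled to occur within 7-14 days after the" last patch application, so the added row includes some undosed days for early terminators. The dose-based measure should stay alongside it for that reason.

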 - The following text shows - **DO NOT APPLY THE PATCHES. YOU **HAVE NOT** REPORTED a qualifying migraine. Please save your answers and return to the diary next time you think you are experiencing a migraine attack.**
- *If a qualifying migraine:*
 - The following text shows - You have reported a qualifying Migraine. Please apply the patches now. **After applying the patches**, press next to answer the remaining questions.
- Where were the study drug patches applied? (Both to left arm, Both to right arm, Other)
 - If Other is checked for above question – the following text shows - You have applied the patches incorrectly. Both patches must be applied. What was the

reason for not applying both? (Applied one patch to left arm, Applied one patch to right arm, Technical problem with applicator and/or patch, None were applied)

Questions at the 30-minute diary post patch application

Please remove the patches from your upper arm, fold in half, and discard

- How bad is your headache pain? (None, Mild, Moderate, Severe)
- Are you nauseated (sick to your stomach)? (Yes, No)
- Did you vomit (throw up)? (Yes, No)
- Does light bother you? (Yes, No)
- Does sound or noise bother you? (Yes, No)
- Since applying the patches, did you take any medication to treat your migraine other than the patches you applied?
- After removing the patches, how much redness do you see on the skin? (None, Mild redness, Moderate colored redness, Beet colored redness)
- After removing the patches, how much swelling do you see? (None, Slight swelling, Moderate swelling, Severe swelling)
- After removing the patches, how much bruising of the skin do you see? (None, Less than a quarter of the application site has bruising spots, About one-half of the application site has bruising spots, More than one-half of the application site has bruising spots)
- After removing the patches, how much bleeding do you see? (None, pink color on skin, visible blood drop, active bleeding)

Post patch application: 2, 12, 24, 48 hours post patch application

- How bad is your headache pain? (None, Mild, Moderate, Severe)
- Are you nauseated (sick to your stomach)? (Yes, No)
- Did you vomit (throw up)? (Yes, No)
- Does light bother you? (Yes, No)
- Does sound or noise bother you? (Yes, No)
- Since applying the patches, did you take any medication to treat your migraine other than the patches you applied? (Yes, No)

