3. STUDY OBJECTIVES

3.1. PRIMARY OBJECTIVE

To assess the long-term safety of 3.8 mg (administered as two 1.9 mg patches) of M207 for the acute treatment of migraine.

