3.3. BRIEF DESCRIPTION

This is an open-label, twelve-month safety study. There is a screening period followed by a run-in period (14 to 21 days) to determine eligibility for treatment with study medication based on daily eDiary data collection. Qualified subjects will receive study medication on Day 1 for up to twelve months for the treatment of migraine headaches. Migraines will be treated with a single dose, consisting of two patches, but subjects can treat multiple migraine attacks throughout the 12 months. Using the eDiary to confirm they are experiencing a qualified migraine, subjects will self-administer the patches and continue to respond to questions in the eDiary for 48 hours post treatment administration.

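### SAP 11.1 credits a one-patch (1.9 mg) application as a full dose, so if such applications occur the dose-count summaries overstate exposure to 3.8 mg by an unknown and possibly negligible amount

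*SAP*

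**What the plan says.** SAP 3.1 gives the primary objective: "To assess the long-term safety of 3.8 mg (administered as two 1.9 mg patches) of M207". SAP 3.3 describes treatment as follows: "Migraines will be treated with a single dose, consisting of two patches". Protocol 3.1 uses the same words.

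SAP 11.1 sets the exposure measure: "Study drug exposure will be captured as the total number of doses". It then gives the counting rule: "a subject is considered as having received one dose regardless if one or two patches are applied". Three summaries rest on that count: "frequencies provided for ≥ 12 doses and ≥ 24 doses", and the number of subjects with "at least 2 doses per month on average for at least 6 months".

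One-patch use is foreseen. In Protocol Appendix 3, a subject who did not put both patches on the same arm selects 'Other', is told the application was incorrect, and chooses from "Applied one patch to left arm, Applied one patch to right arm, Technical problem with applicator and/or patch, None were applied". Protocol 4.5 requires the site to document the reason when both patches were not applied.

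The SAP table index has one exposure table (14.1.1.8), and no title in it refers to the number of patches. Dosing, accountability and eDiary data are listed by subject. SAP section 13, on changes from the protocol, does not mention the counting rule.

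**The concern.** The word dose has two meanings in the SAP: two patches (3.8 mg) in section 3.3, and one or two patches (1.9 or 3.8 mg) in section 11.1. A reader of the exposure table will naturally take a dose to be the 3.8 mg named in the objective. Each one-patch application then counts as 3.8 mg exposure that did not take place.

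At stake is how many subjects can be said to have used 3.8 mg at least 12 times, at least 24 times, or at least twice a month for six months. In a long-term safety study with no comparator, these figures describe how much repeated use the safety data cover. As planned, no summary would show whether the gap between the two meanings is trivial.

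**Working it through.** There is no planned figure to reproduce. SAP 3.5 says the sample size was chosen without statistical considerations, and neither document gives the share of one-patch applications. Call that share *f*. The values below are assumptions.

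**1. What one counted dose can contain.** Two patches give 2 × 1.9 = 3.8 mg and one gives 1.9 mg. Twelve counted doses therefore span 12 × 1.9 = 22.8 mg to 12 × 3.8 = 45.6 mg. Twenty-four span 24 × 1.9 = 45.6 mg to 24 × 3.8 = 91.2 mg. In Protocol Table 1 (Phase 1), one 1.9 mg patch gave 12.3/27.8 = 44% of the two-patch AUC to last measurable concentration, and 7.4/16.4 = 45% of the AUC over 0 to 2 hours.

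**2. Direction.** The SAP count equals two-patch plus one-patch applications. It is never below the two-patch count, so as a count of 3.8 mg doses any error is upward.

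**3. Size for the count.** Overstatement = 1/(1 − f) − 1.

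**4. Size for a subject exactly at a threshold.** With k counted doses, one one-patch use is enough to drop below k full doses. If uses are independent, the probability is 1 − (1 − f)^k.

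| Assumed f | Overstatement of full-dose count | Exactly 12 counted: P(fewer than 12 full) | Exactly 24 counted: P(fewer than 24 full) |
|---|---|---|---|
| 1% | 1/0.99 − 1 = 1.0% | 11% | 21% |
| 5% | 1/0.95 − 1 = 5.3% | 46% | 71% |
| 10% | 1/0.90 − 1 = 11.1% | 72% | 92% |
| 20% | 1/0.80 − 1 = 25.0% | 93% | more than 99% |

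A subject averaging exactly 2 per month over exactly six months has 12 counted doses, so the 12-dose column also applies to the third threshold.

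**5. Size for a subject well above a threshold.** With 18 counted doses, the binomial probability of fewer than 12 full doses is about 0% for f up to 5%, 0.1% at 10% and 5.1% at 20%.

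**6. Who sits near a threshold.** The protocol asks subjects to treat at least 2 migraines a month. Over 6 and 12 months that makes 2 × 6 = 12 and 2 × 12 = 24, the same as the cut-offs. Subjects at the minimum expected use are the ones exposed to the rule.

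Independence is a simplification. If one-patch use clusters in a few subjects, the probabilities in step 4 fall for the same overall f, while a subject who habitually uses one patch could be affected even well above a threshold.

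**The case against.** The strongest reply is that the rule is stated openly, all dosing data are listed, and the size may be negligible. All of that stands. A reader could recount from the listings, but only by hand. The shells for Table 14.1.1.8 are in a separate document and might show a split, although neither the SAP text nor the index calls for one.

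Four stronger readings are tempting and are not supported.

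- **That the study's exposure targets are undermined.** The stated targets are 150 subjects completing six months and 50 completing one year (Protocol 3.2.1, SAP 3.4). They rest on completion and do not use the dose count.
- **That application-site reactions are diluted.** The rule does not feed the adverse event tables. The subject-level skin tables take the worst grade at any time, so including a one-patch attack cannot lower a subject's grade. Only the per-migraine skin tables pool the two kinds of application, through their own denominator. Nor was the dose pattern uniform in the earlier efficacy study: at 1.9 versus 3.8 mg, site pain was 2.3% v 9.6% and erythema 19.5% v 26.5%, but bruise was 13.8% v 14.5%, haemorrhage 5.7% v 4.8% and swelling 3.4% v 2.4% (Protocol Table 8). The protocol also does not say how many patches the 1.9 mg arm wore.
- **That efficacy is misanalysed.** Both documents define mITT to include any amount of study drug. Borrowing the earlier pain-freedom rates, each 10% of one-patch attacks would lower the pooled rate by 0.10 × (41.5 − 27.7) = 1.4 points, which is conservative. Efficacy is secondary and descriptive.
- **That the overstatement should be read in milligrams.** That would be 1/(1 − f/2) − 1, or 0.5%, 2.6% and 5.3% at f = 1%, 5% and 10%. SAP 11.1 plans no milligram total, and the thresholds apply to counts.

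A practical objection also stands: the eDiary alone cannot settle every case. Under 'Other' there is no answer for one patch on each arm, which is two patches, and the technical-problem answer gives no number. Used patches may be discarded (Protocol 4.7), and accountability is by visit (Protocol 4.5), so it will not always assign patches to an attack.

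**Conclusion.** The point holds as a conditional one. SAP 11.1 conflicts with SAP 3.3 and Protocol 3.1 on what a dose is. If one-patch applications occur, the dose count and its three threshold frequencies overstate exposure to 3.8 mg.

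The direction is certain and follows from the rule alone. The size is unknown: 1.0%, 5.3% or 11.1% for the full-dose count at assumed shares of 1%, 5% or 10%. The effect on threshold frequencies falls mainly on subjects close to a cut-off, and the threshold probabilities also assume independent uses. A reader might infer that exposure is materially overstated, but without a one-patch rate the documents do not show that.

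The Safety Population and the count of treated migraines are legitimate on any patch. Treatment duration would change only if a subject's first or last application was a one-patch use. This is a reporting gap worth closing before database lock, and it does not undermine the study's safety analysis.

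**What to change.** In SAP 11.1 and Table 14.1.1.8:

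1. Keep the any-patch count. Beside it, report the number and percentage of applications with two patches, one patch, and patch number unknown.
2. Repeat the three threshold frequencies (at least 12, at least 24, and an average of at least 2 per month for at least 6 months) on confirmed two-patch applications. Add a sensitivity row that counts the unknowns as full doses.
3. Classify eDiary 'Other' entries from site source records and patch accountability where possible, and show the rest as unknown. No extra rule is needed when no patch was applied, because the existing rule credits a dose only for one or two patches.
4. Reconcile the meaning of a dose in SAP 11.1 with SAP 3.3.
5. Optionally, add a descriptive two-patch-only row to the per-migraine pain-freedom and most-bothersome-symptom tables, leaving mITT as defined.

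The cost is a revised paragraph, one derived variable, and some work on 'Other' entries, which may need source information that is not in the database. Stated exposure may come out slightly lower. If one-patch use proves rare, the table will show it and the exposure statement will be stronger.
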